5.8 Abdominal Pain

Descriptive summaries of the following categories will be presented, if applicable:

- Abdominal pain pattern (“No pain”, “Episodes of mild/moderate pain-but no constant pain”, “Constant mild/moderate pain-but no episodes”, “Episodes of severe pain-but no constant pain”, “Constant mild/moderate pain plus episodes of more severe pain”, “Constant severe pain”)

USA

- Average episodic abdominal pain intensity (0 – 10 numerical rating scale)
- Worst episodic abdominal pain intensity (0 – 10 numerical rating scale)
- Frequency of episodes of abdominal pain (number of abdominal pain episodes last month)
- Episode typical duration (“A few hours”, “More or less a day”, “Several days”, “More than a week”)
- Abdominal pain triggers (“High-fat meals”, “Stress”, “Alcohol”, “Tobacco”, “Physical activity”, “Other”)
- Abdominal pain lasting period before enrolment (“Less than 3 months”, “between 3 and 6 months”, “longer than 6 months”)
- Abdominal pain relief methods (“OTC pain medication”, “Rest”, “Fasting and/or adjusting diet”, “Bowel movement”, “Other”)
- Abdominal pain control (“Yes”, “No”)
- Abdominal pain severe enough to seek medical attention (“Primary healthcare provider”, “Specialist”, “Emergency room”, “Urgent care”, “Hospital”)
- Hospitalization due to abdominal pain (“Less than 24 hrs”, “A few days”, “A week”, “More than a week”)

5.9 Gastrointestinal Symptoms

Descriptive summaries of the following categories will be presented, if applicable:

- Level of bloating over the past week (“None”, “Mild”, “Moderate”, “Severe”, “Very Severe”)
- Level of flatulence over the past week (“None”, “Mild”, “Moderate”, “Severe”, “Very Severe”)
- Level of nausea over the past week (“None”, “Mild”, “Moderate”, “Severe”, “Very Severe”)
- Number of bowel movement per day over the past week

USA

- Number of urgency episodes over the past week (“Never”, “One time”, “A few times”, “Once per day”, “Multiple times per day”)
- Steatorrhea (stool look oily, smelled really bad, and/or floated/was difficult to flush) over the past week (“Never”, “Rarely”, “Some of the time”, “Often”, “All the time”)
- Stool consistency over the past week (Type 1 – 7)

5.9.1 Bristol Stool Form Scale (BSFS)

The BSFS is used for classifying the form of stool into 7 categories scored from 1 to 7:

1. Separate hard lumps like nuts (difficult to pass)
2. Sausage-shaped but lumpy
3. Like a sausage but with cracks on its surface
4. Like a sausage or snake, smooth and soft
5. Soft blobs with clear-cut edges (passed easily)
6. Fluffy pieces with ragged edges, a mushy stool
7. Watery, no solid pieces, entirely liquid

5.10 Dietary Habits

Descriptive summaries of the following categories will be presented, if applicable:

- Type of diet (“Vegetarian”, “Mostly vegetarian with occasional meat”, “Meat/poultry a few times/week”, “Daily poultry/meat”, “Vegan”, “Gluten-free”, “Low FODMAP”, “Diabetic”, “Other”)
- Number of meals/snacks per day
- Amount of fat in diet per day (“High in fat”, “Average fat”, “Low in fat”)
- Frequency of sweets intake (“Never”, “Once a week”, “A few times per week”, “Once a day”, “A few times a day”)
- Frequency of dietary restrictions to avoid symptoms (“Never”, “Rarely”, “Some of the time”, “Often”, “All the time”)

USA

5.11 Health-Related Quality of Life

HRQOL will be measured using the 12-item Short Form Survey (SF-12). 10 of the 12 questions are answered on a 5-point Likert scale and 2 are answered on a 3-point Likert scale. The questions are then scored and weighted into 2 subscales, physical health and mental health. Respondents can have a score that ranges from 0 – 100 with 100 being the best score and indicating high physical or mental health. A 3-point change in SF-12 score reflects a meaningful difference. The methodology used to transform raw scores to 100 scale is based on [2].

Descriptive statistics per subscale will be provided to summarize health-related quality of life. Patients' response will also be listed.

5.12 Anxiety/Depression

Anxiety and depression levels will be measured with the Hospital Anxiety and Depression Scale (HADS). The HADS consists of 14 items divided into two 7-item subscales: Anxiety (HADS-A) and depression (HADS-D). Respondents rate each item on a 4-point scale from 0 (absence) to 3 (extreme presence). The total score is 42 (21 per subscale). Scores are derived by summing responses for each of the two subscales or for the scale as a whole. Higher scores indicate greater levels of anxiety and depression.

Descriptive statistics per subscale will be provided to summarize patients' anxiety/depression level. Patients' response will also be listed.

5.13 Healthcare utilization

Healthcare utilization data will be assessed in terms of the impact and burden of EPI due to CP on the healthcare system.

Descriptive summaries of the following categories will be presented, if applicable:

- Number of healthcare provider
- Number of ER

USA

- Number of telephone/health visits
- Hospitalizations and length of stay
- Number of sick days, if employed in the past 6 months

5.14 COVID-19 information

Descriptive summaries of the following categories will be presented, if applicable:

- If the patient is diagnosed with COVID-19
- COVID-19 Symptoms (“Fever or chills”, “Cough”, “Shortness of breath or difficulty breathing”, “Fatigue”, “Muscle or body aches”, “New loss of taste or smell”, “Sore throat”, “Congestion or runny nose”, “Nausea or vomiting”, “Diarrhea”, “N/A”)
- If the patient is vaccinated
- COVID-19 vaccine-associated side effects (“Tiredness”, “Headache”, “Muscle Pain”, “Chills”, “Fever”, “Nausea”, “N/A”)

5.15 Exploratory Analysis

Multivariate modeling will be employed to study both the EPI due to CP disease history and disease progression. The coefficients across the different models will be provided. P-value of exact F statistics test comparing the coefficients among different variables may also be provided.

Potential dependent variables are:

- Clinical manifestations of EPI (“Diarrhea/loose stool”, “Steatorrhea”, “Abdominal pain”, “Bloating”, “Flatulence”, “Unintentional weight loss/difficulty gaining weight”, “Malnutrition”, “Vitamin D deficiency”, “Other vitamin/mineral deficiencies”)
- How have enzymes been impacting the symptoms (“Greatly improved symptoms”, “Somewhat improved symptoms”, “Symptoms are unchanged”, “Somewhat worsened my symptoms”, “Greatly worsened my symptoms”)

USA

- The patient's chronic pancreatic etiology ("Toxic-Metabolic", "Metabolic", "Idiopathic", "Genetic", "Autoimmune", "Recurrent and severe acute pancreatitis", Obstructive, "Other")
- Evidence of suspected/confirmed EPI diagnosis ("Abnormal fecal elastase -1 test", "Clinical steatorrhea", "Vitamin deficiency", "Weight loss", "Pancreatic function testing", "Other")
- Abdominal pain pattern ("No pain", "Episodes of mild/moderate pain", "Constant mild/moderate pain", "Episodes of severe pain", "Constant mild/moderate pain plus episodes of more severe pain", "Constant severe pain")
- Health-Related Quality of Life
- Treatment compliance

Potential independent variables are:

- Type of PERT (Creon®, Pancreaze®, Pertzye®, Viokase®, Zenpep®, Other)
- Medical History
- Comorbidities (simultaneous presence of two or more diseases or medical conditions)
- PERT Dose at initiation
- PERT Dose escalation
- Recommendation on how to take PERT ("Entire dose at the beginning of meal", "Half before the meal and the other half during the meal", "Entire dose 20 minutes before the meal", "PERT should be taken with meals only", "PERT should be taken within meals and snacks", "Other")
- Reason for switching to another PERT ("Efficacy", "Dosing", "Insurance coverage", "Patient preference", "Physician preference", "Other")

Healthcare utilization rate may be calculated based on

- Number of healthcare providers
- Number of ER visits

USA

- Number of tele health visits
- Hospitalizations and length of stay
- Number of sick days, if employed in the past 6 months

Potential confounders will be explored for predicting outcomes with the registry data. If any confounding is identified, statistical procedures such as stratified analysis, multivariable analysis, and/or sensitivity analysis may be employed as appropriate for that confounder and outcome.

USA**6 APPENDICES****6.1 Appendix A – Eligible PERT**

Drug Type	Non-Proprietary Name	Brand Name
Pancreatic Enzyme Replacement Therapy	Pancrelipase	Zenpep®
	Pancrelipase	Creon®
	Pancrelipase	Pancreaze®
	Pancrelipase	Pertzye®
	Pancrelipase	Viokase®

USA

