3 STUDY DESIGN

3.1 Overall Design

This is a prospective, non-interventional study for individuals with EPI due to CP who are under the care of a gastroenterologist. Longitudinal data will be collected from both study participants as well as from their clinical encounters with their treating gastroenterology providers using a structured and standardized data collection method. The scope of data collection (see [Table 1](#)) from the study participants includes demographics, current work status, current insurance coverage, family disease history, weight/height, current over the counter (OTC) herbal/nutritional supplements, healthcare utilization, and PROs on abdominal pain, GI symptoms, dietary habits, health-related quality of life, depression/anxiety, and PERT use and treatment satisfaction. At the time of routine clinical encounters, Investigators complete assessments on medical history, information on suspected/confirmed EPI diagnosis, CP etiology, clinical manifestations of EPI (GI and nutritional manifestations), AEs, and current treatment(s).

This is a 5-year study with an anticipated first enrollment date of 01 April 2021. The total enrollment period will be 24 months in length and data collection and study close-out will take place 3 months prior to the anticipated study end date. The study duration from enrollment to study end is five (5) years.

Study data will be collected from Investigators at the time of routine clinical encounters, as well as from study participants remotely in between routine visits.

Enrollment

Study participants will be enrolled in the study if they meet eligibility criteria and after they have provided consent to participate. During the Enrollment Visit, the Investigator will confirm eligibility and will provide information on suspected/confirmed EPI diagnosis (date of diagnosis, date of onset of symptoms indicative of EPI, method of EPI diagnosis, if applicable), CP etiology, clinical manifestations of EPI (i.e., GI and nutritional manifestations), medical history (comorbidities, surgical and radiological procedures, endoscopic procedures, and laboratory abnormalities), and current treatment(s). Information collected from the study participant

USA

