includes demographics, current work status, current insurance coverage, family disease history, weight/height, current over the counter (OTC) herbal/nutritional supplements, healthcare utilization, and participant-reported outcome assessments on abdominal pain, GI symptoms, health-related quality of life, depression/anxiety, and PERT use and treatment satisfaction.

Follow-Up

Follow-up data will be collected from the study participants remotely via electronic data capture (EDC) portal. Every 3 months, study participants will complete assessments on current work status, current insurance coverage, current weight, current OTC herbal/nutritional supplements, and abdominal pain, GI symptoms, and PERT use and treatment satisfaction. Every 6 months, in addition to the assessments completed every 3 months, study participants will also complete assessments on health-related quality of life, depression/anxiety, and healthcare utilization.

The Investigator will provide updates during routine clinical encounters approximately every 6 months or at least 150 days from the last registry visits. Data will be collected on clinical manifestations of EPI, current treatment(s), and active assessment of adverse events/serious adverse events (AEs/SAEs) since last visit. “Early” follow-up visits will be conducted whenever a study participant is prescribed a new PERT product. The Investigator will not complete any assessments if the study participants do not return to the sites for their expected routine clinical encounter.

Study Participant Exit

Study participants exit the study upon withdrawal from the study, lost to follow-up (LT FU), transfer of care to a different gastroenterologist, death, or any other reason resulting in a study participant’s exit. The Investigator will document the reason for the exit.

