5.3 Demographic and Baseline Characteristics

Demographic and baseline characteristics will be collected during the enrollment visits (See [Table 1](#)). Descriptive summaries of demographics and other baseline characteristics in the following categories will be presented for all enrolled population.

- Age
- Gender (“Woman”, “Man”, “Other”, “Prefer not to say”)
- Ethnicity (“Hispanic or Latino”, “Not Hispanic or Latino”)
- Race (“American Indian or Alaska Native”, “Native Hawaiian or Other Pacific Islander”, “Asian”, “Black or African American”, “White”, “Other”)
- Marital status (“Single”, “Married/Partnered”, “Divorced/Separated”, “Windowed”)
- Highest level of education (“High school, not completed”, “High school, completed”, “University, no degree”, “Associate or equivalent”, “Bachelor’s or equivalent”, “Master’s or equivalent”, “PhD or equivalent”)
- Annual household income
- Residence setting (“Rural”, “Suburban”, “Urban”)
- Current insurance coverage (“Insurance through a current or former employer or union”, “Insurance purchased directly from an insurance company”, “Medicare”, “Medicaid”, “TRICARE or other military healthcare”, “VA”, “Indian Health Service”, “Other type of insurance or health coverage plan”, “No insurance”)
- Current work status (“Full-time employed”, “Part-time employed”, “Retired”, “Unemployed, looking for work”, “Unemployed, unable to work”, “Student”)
- Height/weight (current weight, highest weight ever, unintentional weight loss)
- Family history of pancreatic disease, pancreatic cancer, pancreatic resection, celiac disease, and diabetes
- Current OTC herbal/nutritional supplements

USA

- The patient's chronic pancreatic etiology ("Toxic-Metabolic", "Metabolic", "Idiopathic", "Genetic", "Autoimmune", "Recurrent and severe acute pancreatitis", Obstructive, "Other")
- Evidence of suspected/confirmed EPI diagnosis ("Abnormal fecal elastase -1 test", "Clinical steatorrhea", "Vitamin deficiency", "Weight loss", "Pancreatic function testing", "Other")
- Clinical manifestations of EPI ("Diarrhea/loose stool", "Steatorrhea", "Abdominal pain", "Bloating", "Flatulence", "Unintentional weight loss/difficulty gaining weight", "Malnutrition", "Vitamin D deficiency", "Other vitamin/mineral deficiencies")

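### SAP 5.15: the only named test depends on measurement units if read as written, two enrollment-only variables are listed as outcomes, and the site grouping promised in Protocol 11 is not carried over

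*SAP*

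**What the plan says.** SAP 5.15 states its purpose as "Multivariate modeling will be employed to study both the EPI due to CP disease history and disease progression". It then says "The coefficients across the different models will be provided" and adds the one test it names: "P-value of exact F statistics test comparing the coefficients among different variables may also be provided".

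Seven potential dependent variables follow: clinical manifestations, perceived enzyme impact, CP etiology, evidence of EPI diagnosis, abdominal pain pattern, health-related quality of life and treatment compliance. The seven potential independent variables include PERT type, initial dose, dose escalation, comorbidities and reason for switching PERT. The section gives no model family, row definition (participant or visit), time, baseline or change term, or site term.

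Other sections bear on this:
- **Enrollment data.** SAP 3.1: "During the Enrollment Visit, the Investigator will confirm eligibility and will provide information on suspected/confirmed EPI diagnosis". CP etiology is in the same list, and Table 1 marks both items once, under Enrollment. SAP 5.3 reports both among the characteristics of which it says "Demographic and baseline characteristics will be collected during the enrollment visits".
- **Follow-up data from the investigator.** SAP 3.1: "Data will be collected on clinical manifestations of EPI, current treatment(s), and active assessment of adverse events/serious adverse events (AEs/SAEs) since last visit". Neither etiology nor diagnosis evidence appears.
- **Change.** SAP 5.1 offers descriptive shift tables for categorical variables, where applicable. SAP 5.11 says "A 3-point change in SF-12 score reflects a meaningful difference".
- **Grouping.** Protocol 11 commits to ANOVA models for grouping by site, practice or physician, and leaves the complete analysis details to the SAP.

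**The concern.** SAP 5.15 is the only modelling section in the SAP; the rest is descriptive. The specific aims on disease progression and on the effect of care patterns therefore rest on it. Three of its features would mislead if followed as written.

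1. A test comparing coefficients of different variables invites the reader to rank factors by importance, yet coefficients on different scales are not comparable.
2. A variable fixed at enrollment cannot progress. Pairing it with a dose escalation or PERT switch that happens later puts the predictor after the outcome.
3. Participants at one site may share both prescribing habits and outcomes. If site is left out, some p-values will be too small.

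Progression, the stated target, also has no modelled quantity. A 3-point SF-12 change is called meaningful, but no model term measures change.

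**Working it through.** The plan gives no effect size, SD, correlation or dropout figure, and sets the target of 400 by judgment, so it has no figure of its own to reproduce here. From the documents: n = 400 and about 20 sites, hence 20 participants per site. All other inputs below are assumptions.

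**1. Equality of two coefficients.** Assume outcome SD 10, a comorbidity indicator with SD 0.5 and a true effect of 3 points, a dose with SD 20,000 units and no effect, and uncorrelated predictors. The standard error of a coefficient is 10 / (√400 × SD of the predictor). For comorbidity it is 10 / (20 × 0.5) = 1.000. The expected difference between the two coefficients is 3 in every row, because the dose effect is zero.

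| Dose unit | SD in that unit | SE of dose coefficient | SE of difference | Rejection at 5% |
|---|---|---|---|---|
| 1,000 | 20 | 0.025 | 1.000 | 85.1% |
| 10,000 | 2 | 0.25 | 1.031 | 82.9% |
| 25,000 | 0.8 | 0.625 | 1.179 | 72.0% |
| 100,000 | 0.2 | 2.5 | 2.693 | 20.0% |

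SE of difference = √(1.000² + SE of dose coefficient²). Rejection = Φ(3/SE − 1.96) + Φ(−3/SE − 1.96).

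A single simulated data set of 400 shows the same thing. The equality p-value was 0.255 with dose in units, 0.135 in thousands and 0.0036 in ten-thousands. The joint test that all coefficients are zero gave 0.060 each time, and the test of dose alone gave 0.0071 each time. If the comparison is instead of one predictor's coefficients across two outcomes, p moved from 0.0075 to 0.519 when the second outcome was multiplied by 20. Wilks' exact F for a joint zero effect stayed at 0.0234.

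**2. Time order.** SAP 3.1 describes a 5-year study in which "data collection and study close-out will take place 3 months prior to the anticipated study end date". The earliest enrollee can thus be followed for 60 − 3 = 57 months. Escalation or switching may be recorded at any point in that time. Etiology and diagnosis evidence are recorded once, at Day 0.

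**3. Site omitted.** The design effect is 1 + (20 − 1) × ICC of outcome × ICC of predictor. The actual error of a nominal 5% test is 2[1 − Φ(1.96/√design effect)].

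| Outcome ICC | Predictor constant within site (ICC 1) | Predictor ICC 0.3 | Predictor ICC 0.02 |
|---|---|---|---|
| 0.01 | 7.2% | 5.7% | 5.0% |
| 0.05 | 16.0% | 8.4% | 5.2% |
| 0.10 | 25.0% | 11.8% | 5.4% |

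**4. A check on the remedy.** Adjusting every repeated outcome for its Day 0 value looks natural, but Protocol 5.2 admits participants already on PERT. Suppose a 3-point effect is already present at Day 0 and persists. With participant SD 7, the coefficient on the Day 0 value is 49/(49 + 25) = 0.66 for residual SD 5 and 49/(49 + 49) = 0.50 for residual SD 7. The adjusted effect is 3 × (1 − 0.66) ≈ 1.0 or 3 × (1 − 0.50) = 1.5. Most of the effect is adjusted away.

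**The case against.** The best defence is that the section is exploratory, its variables are only potential and its p-value is optional. That stands and limits the severity. It does not rescue a test whose answer changes with the unit of dose.

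Multivariate modelling with an exact F may mean a joint-zero test such as Wilks', which is free of units. That is plausible, so the unit problem belongs to the equality reading. But the sentence speaks of comparing coefficients among variables and never states a zero hypothesis.

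The section also covers disease history, for which etiology and diagnosis evidence are legitimate subjects. That stands. No pairing of outcome with predictor is fixed, so the reversed time order is permitted, not prescribed.

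Some stronger inferences are not supported:
- **That visits will be pooled as independent rows.** With 6 to 10 rows per participant and a within-participant correlation of 0.3 to 0.7, this would give 22-47% error for a participant-level predictor. The SAP does not say rows will be pooled; it does not say what a row is.
- **That clustering by site was overlooked.** Protocol 11 addresses it. The gap is that the SAP does not carry it over.
- **That error will reach 25%.** This needs a predictor constant within site and an ICC of 0.10, and no listed predictor is defined at site level.
- **That change is ignored altogether.** SAP 5.1 plans shift tables, and displays by visit may sit in the separate TFL document. Neither is a model of progression.

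**Conclusion.** The point holds as three specific defects and one omission in an exploratory section, and should be fixed before the SAP is finalized.

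- **Test.** Under the equality reading, rejection ran from 85% to 20% with the choice of dose unit alone. The size rests on assumed SDs and effects; the dependence on units does not.
- **Outcomes.** Etiology and diagnosis evidence cannot show progression and should not be modelled on later treatment changes. This follows from Table 1 and needs no assumption.
- **Site.** For assumed outcome ICCs of 0.01-0.10, omitting site gives 7-25% error for a predictor constant within site, 6-12% for a predictor ICC of 0.3, and about 5-6% for a predictor nearly unrelated to site.
- **Progression.** No time or change term is modelled.

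It would be too much to infer that the registry's conclusions are unsound. Most of the plan is descriptive and is untouched by this.

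**What to change.** Amend SAP 5.15 as follows.

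1. Replace the F test across variables with a Wald or likelihood-ratio test that each term, all its levels jointly, is zero. Use a model suited to the outcome scale: for example linear for the SF-12 subscales, logistic for each manifestation and ordinal for enzyme impact. Give 95% confidence intervals and label p-values as unadjusted.
2. Use etiology and diagnosis evidence as baseline covariates or as descriptive disease-history variables. State that they will not be regressed on later escalation or switching.
3. Carry the grouping in Protocol 11 into SAP 5.15 as a site effect. Make it random where a predictor is constant within site, since a fixed site effect would absorb that predictor.
4. For repeated outcomes, state that rows are visits. Include a participant random effect (or participant-clustered standard errors) and time since enrollment, and use a predictor-by-time term where progression is the question.
5. Do not require Day 0 adjustment for exposures that may predate enrollment. Limit it to participants newly prescribed PERT at enrollment, or to predictors arising after Day 0.

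The cost is rewording, modest extra programming and somewhat wider confidence intervals. No new data are needed.

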11. DATA ANALYSIS

Statistical analyses will be guided by the specific aims of the registry. Complete details of all analyses will be described in a standalone Statistical Analysis Plan (SAP) with accompanying mock Tables, Figures and Listings (TFLs).

All data will be summarized descriptively. Continuous variables will be described through reporting of the mean (\pm standard deviation), median and range, while categorical data will be described through reporting of frequency and percent. The participant population will be characterized by demographics and baseline attributes. From this characterization, important subgroups of interest may be identified if sample sizes are sufficiently robust for additional exploratory analyses. All pre-planned, clinically important subgroups for analyses will be identified in the SAP.

Study disposition of all participants will be summarized including dropouts (with reasons presented for those who drop out), and for lost to follow-up (at what point they are lost, and if they return).

Multivariate modeling will be employed to study both the EPI due to CP disease history and disease progression by analyzing patterns of medical history, comorbidities, and treatment approaches. Variables in the modeling will also include clinical care practices and their impact on the modeling.

Clinical care practices will be further explored with their potential impact on quality of life, comorbidities, and treatments using the same multivariate modeling. Treatment compliance will be examined for each of the models, knowing that biases are introduced with participant recall. Prescribing practices will be descriptively presented (to include type of PERT, dose at initiation and escalation, recommendation on how to take PERT, and reason for switching to another PERT, if applicable). If trends are identified in prescribing patterns, these trends may be further explored.

Healthcare utilization data will be assessed with key variables from the clinical dataset. Impact and burden of EPI due to CP will be assessed for impact on the healthcare system (the number of ER visits, healthcare provider visits, number of hospitalizations, length of hospital stay, and number of sick days taken). Associations will be presented descriptively, and if the data are robust, inferential statistics will be presented using rates and 95% confidence intervals.

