5.5 PERT and other supplement/medication/therapies

Patients are considered as compliant if they are kept on PERT during the study. The eligible PERTs are listed in [Appendix A](#). If any patient answers "No" to the question "Do you take your

USA

enzymes everyday?” two times for two consecutive timepoints, , the patient is considered as noncompliant.

Descriptive summaries of the following categories will be presented, if applicable:

- Type of PERT (Creon®, Pancreaze®, Pertzye®, Viokase®, Zenpep®, Other)
- PERT Dose at initiation
- PERT Dose escalation (“Yes”, “Not Applicable”)
- PERT Dosing frequency per day
- Number of pills of PERT taken per day
- Habit when taking PERT (“With my meals only”, “With my snacks only”, “With my meals and snacks”, “Outside of my meals/snacks”, “Other”)
- PERT Route of administration (“Oral”, “Enteral feeding tube”, “Other”)
- Recommendation on how to take PERT (“Entire dose at the beginning of meal”, “Half before the meal and the other half during the meal”, “Entire dose 20 minutes before the meal”, “PERT should be taken with meals only”, “PERT should be taken with meals and snacks”, “Other”)
- Reason for switching to another PERT (“Efficacy”, “Dosing”, “Insurance coverage”, “Patient preference”, “Physician preference”, “Other”)
- How have enzymes been impacting the symptoms (“Greatly improved symptoms”, “Somewhat improved symptoms”, “Symptoms are unchanged”, “Somewhat worsened my symptoms”, “Greatly worsened my symptoms”)
- Type of vitamins and antioxidants (“Fat soluble vitamin supplement or repletion”, “Vitamin B 12 supplement”, “Zinc”, “Calcium”, “Probiotics”, “Other”)
- Type of pain medications (“Opioids”, “Simple analgesics”, “Tramadol”, “Non-steroidal anti-inflammatory drugs”, “Gabapentin”, “Cannabinoid”, “Other”)
- Type of neuromodulators (“Selective Serotonin Reuptake Inhibitors”, “Serotonin and Norepinephrine Reuptake Inhibitors”, “Tricyclic Antidepressants”, “Monoamine Oxidase Inhibitors”, “Atypical Antidepressants”, “Other”)

USA

- Type of Antidiarrheals (“Lomotil”, “Imodium”, “Other”)
- Type of other medication (“Insulin”, “Metformin”, “Other antidiabetic medications”, “Proton pump inhibitors”, “H2 blockers”, “Other”)
- Type of other therapies (“Dietician consultation”, “Other nutritional support/management”, “Cognitive behavioural therapy”, “Other”)

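### SAP 5.15 lists PERT dose escalation and reason for switching as predictors of symptoms and quality of life with no time order, so decisions that respond to symptoms can look like harm

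*SAP*

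**What the plan says.** Aim 3 asks how differing care practices affect outcomes. Protocol 11 carries this into the analysis: "Clinical care practices will be further explored with their potential impact on quality of life, comorbidities, and treatments using the same multivariate modeling".

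SAP 5.15 sets up the models. Under "Potential dependent variables are" it names clinical manifestations of EPI, "How have enzymes been impacting the symptoms", abdominal pain pattern and "Health-Related Quality of Life", among others. The potential independent variables include "PERT Dose escalation" and "Reason for switching to another PERT", the latter with six categories, one of which is Efficacy. Coefficients are to be provided; a p-value from an F test is optional.

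No visit, date order, lag or adjustment for an earlier outcome value is given for any pairing. SAP 5.5 codes escalation as "PERT Dose escalation (“Yes”, “Not Applicable", with no date shown. The switch-reason variable has no category for participants who never switch, and SAP 5.1 rules out imputation.

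Two passages bear on confounding. Protocol 11 names confounding by indication, illustrated by who receives experimental or newer treatments. The end of SAP 5.15 says that stratified, multivariable or sensitivity analyses may be used if confounding is identified.

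**The concern.** Escalation and switching happen during follow-up, and poor symptom control is a plausible trigger for both. The Background section of the Protocol says that dosing is hard to settle because response varies between patients. Under Protocol 6.3.3 a prescription for another PERT qualifies a visit as an early follow-up, and clinical manifestations are recorded at on-site visits. A switch and the symptoms behind it can therefore be recorded together. A switch for Efficacy is in substance a statement about the outcome.

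Without time order, the model tests whether escalation is associated with symptoms. Aim 3 asks whether escalation changes symptoms. If clinicians react to symptoms, there is an association even when escalation changes nothing. Adjusting for the enrollment value removes only part of it, because the trigger is the symptom state later in follow-up. The registry could then report escalation, or switching for efficacy, as going with worse pain and quality of life when the worse state came first.

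**Working it through.** **Inputs from the documents.** N is about 400, set by judgment (SAP 3.3). A 3-point SF-12 change is meaningful (Protocol 7.5.4, SAP 5.11). SAP 5.15 states no alpha, effect size or model form, so there is no plan figure to reproduce.

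**Assumptions.** Two-sided 5% test. About 30% escalate, about 12% switch for Efficacy, and some others switch for the remaining reasons. The odds of escalating or of switching for Efficacy rise by OR per 1 SD worse health at the decision. The correlation between health at the decision and the later outcome is rho. No care practice has any effect.

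**Step 1: approximate size of the spurious gap.** If the odds rise by OR per SD, escalated and non-escalated participants differ by about ln(OR) SD at the decision and about rho × ln(OR) SD later. With 120 escalated and 280 not, SE = √(1/120 + 1/280) = 0.109 SD. Rejection ≈ Φ(gap/SE − 1.96) + Φ(−gap/SE − 1.96).

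- OR 1.25, rho 0.3: gap 0.3 × 0.223 = 0.067; z = 0.61; about 9%.
- OR 1.5, rho 0.6: gap 0.6 × 0.405 = 0.243; z = 2.23; about 61%.
- OR 2, rho 0.6: gap 0.6 × 0.693 = 0.416; z = 3.81; about 97%.

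If the SF-12 SD is 10 (assumed), the middle case is a non-causal gap of about 2.4 points, close to the 3 points the plan calls meaningful. A full 3-point non-causal gap gives z = 0.30/0.109 = 2.75, which is significant about 79% of the time.

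**Step 2: simulation under no effect** (2,000 runs per row, N = 400). The last two columns test all care practices jointly on the later outcome, adjusted for its value at the decision.

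| OR | rho | Escalation | Switch reason | All practices jointly | Joint, adjusted | Joint, adjusted; earlier value has reliability 0.7 |
|---|---|---|---|---|---|---|
| 1 | 0.6 | 4.8% | 5.6% | 5.0% | 4.8% | 5.4% |
| 1.25 | 0.3 | 10.6% | 5.1% | 7.4% | 5.2% | 5.2% |
| 1.25 | 0.6 | 23.8% | 8.0% | 14.2% | 4.9% | 6.6% |
| 1.5 | 0.6 | 57.8% | 17.6% | 42.3% | 5.6% | 8.6% |
| 2 | 0.6 | 93.8% | 48.8% | 89.6% | 4.6% | 15.9% |
| 2 | 0.8 | 99.8% | 78.0% | 99.6% | 5.5% | 33.6% |

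A care practice unrelated to symptoms stayed at 4.6% to 5.8% throughout, so the bias falls on the reactive predictors. At OR 1.5 and rho 0.6, a test that two coefficients are equal rejects 33.2%. Efficacy against other reasons, among switchers only, rejects 25.4%.

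**Step 3: repeated visits.** Assume seven six-monthly assessments, a stable-patient share of variance of 0.3, autocorrelation of 0.5 in the rest, and first escalation only, counted before the final assessment. Rejection under no effect, N = 400:

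| Model | OR 1.25 | OR 1.5 | OR 2 |
|---|---|---|---|
| Final score on ever-escalated | 18% | 45% | 92% |
| The same, plus baseline score | 11% | 19% | 54% |

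A lagged model (next score on escalation, adjusted for the current and baseline scores, in those not yet escalated) rejects 3% to 5%.

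**Step 4: a real benefit.** With a true benefit of 0.2 SD, the Step 1 approximation gives an expected coefficient of 0.2 − 0.067 = +0.133, 0.2 − 0.243 = −0.043 and 0.2 − 0.416 = −0.216 SD in the three cases: reduced, about zero and reversed. In the repeated-visit simulation the ever/never model likewise gave about zero or the wrong sign, while the lagged model recovered the benefit.

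**The case against.** The section is headed exploratory, the variables are only potential ones, the p-value is optional and no alpha is stated. This stands: no fixed model or error rate is breached. Coefficients are still to be provided, though, and their bias does not depend on whether a p-value is printed.

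The sponsor has seen the neighbouring problem, since Protocol 11 names confounding by indication. This stands in part. The example concerns who receives newer treatments, the remedies are conditional, and neither document considers a predictor set off by the outcome during follow-up.

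Four stronger readings are tempting, and the documents do not support them.

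- *Both predictors are always reactions to symptoms.* Insurance coverage as a switch reason is not, by its wording, such a reaction, and the documents do not say why doses are escalated.
- *The test will reject almost regardless.* No escalation rate, reactivity or persistence is given, and in the mildest settings rejection is close to nominal.
- *A switch for Efficacy and the enzyme-impact answer are the same judgement.* Enzyme impact is reported by the participant (Protocol 7.5.6) and treatments by the Investigator (Protocol 7.3). The documents do not say who supplies the switch reason, and a later impact answer may concern the new product.
- *Aim 3 will get an answer with the wrong sign.* That needs a real benefit smaller than the bias. It is possible, not established.

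A lagged model is not a full cure either. It returns to 5% only when the recorded earlier value captures what drove the decision. With reliability 0.7 for that value, the joint test still rejects 8.6% to 33.6% over OR 1.5 to 2 and rho 0.6 to 0.8.

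**Conclusion.** The concern holds in conditional form. To the extent that escalation and switching respond to symptoms, the SAP 5.15 coefficients for these predictors lean toward apparent harm and can hide a benefit, and any F test on them rejects too often. Under no effect and N = 400, rejection runs from about 5% (switch reason) to 18% (final score on ever-escalated, repeated visits) in the mildest settings at OR 1.25. It exceeds 90% for escalation at OR 2 with rho of 0.6 or more. These rates rest on assumed reactivity, persistence and escalation rates; only the sample size comes from the plan. The existing confounding text does not remove the problem. Because Aim 3 and Protocol 11 speak of impact, the change is worth making even in an exploratory section.

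**What to change.** In SAP 5.15:

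1. Do not use reason for switching as a predictor of symptoms, enzyme impact, pain or quality of life. Keep it in the SAP 5.5 descriptive summary. This also avoids a complete-case model that would retain only switchers. It need not be barred from models of other outcomes such as treatment compliance, provided that a no-switch category is defined there.
2. For those same outcomes, enter dose escalation only as a lagged exposure. Take the outcome from the next assessment after the escalation, in participants not previously escalated. Adjust for the last recorded outcome value before the escalation and for the baseline value, and use participant-clustered standard errors. State how the escalation is dated from the on-site treatment records, because SAP 5.5 shows only a yes or not-applicable code.
3. Label all such results as associations, and state that confounding by unrecorded or imperfectly measured reasons for the decision remains.

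The cost is SAP text and a derived lag variable. No new visits or participants are needed, provided that the treatment records allow escalations to be placed in time. Participant-reported outcomes recur every 3 or 6 months, while treatments are recorded at separately scheduled on-site visits. Some escalations will therefore lack an earlier or a later assessment and drop out, which widens the intervals.
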